## 2 SAMPLE SIZE DETERMINATION

The primary endpoint is the proportion of participants with WI-NRS reduction of  $\geq 4$  from baseline to Week 12. By assuming the response rate is [REDACTED] in the placebo and dupilumab arms, respectively, 56 participants/arm will provide 90% power to detect the difference of [REDACTED] between dupilumab and placebo with Fisher exact test at 2-sided level of 0.05. Assuming 15% drop out during the 12 weeks of treatment, the target is to randomize 75 participants/arm with a cap of up to 10% of participants in the atopic population having active mild AD.

The assumptions were based on the effect of dupilumab versus placebo in WI-NRS reduction  $\geq 4$  at Week 16 observed in participants with moderate to severe AD as seen in studies of AD-1334 (Solo1) and AD-1416 (Solo2).

Approximately 150 participants will be randomized to dupilumab or placebo in a 1:1 ratio with stratification factors of documented history of atopy (atopic or non-atopic), stable use of TCS/TCI (yes or no), and country/territory code. Both the atopic and the non-atopic PN population will be capped at 60% of the total enrolled population.

The sample size calculation was performed using SAS 9.4 power procedure.

### 3 ANALYSIS POPULATIONS

The following populations for analyses are defined:

**Table 4 - Populations for analyses**

Population	Description
Screened	All participants who sign the ICF.
Randomized	The randomized population includes all participants with a treatment kit number allocated and recorded in the interactive response technology (IRT) database, and regardless of whether the treatment kit was used or not. Participants treated without being randomized will not be considered randomized and will not be included in any efficacy population.
Intent-to-treat (ITT)	All randomized participants analyzed according to the intervention group allocated by randomization regardless if treatment kit is used or not
Efficacy	The ITT population
Safety	All participants randomly assigned to study intervention and who take at least 1 dose of study intervention. Participants will be analyzed according to the intervention they actually received. Randomized participants for whom it is unclear whether they took the study medication will be included in the safety population as randomized. For participants who accidentally receive different treatment from the planned, the actual intervention allocation for as-treated analysis will be the dupilumab group. The PD analyses will be performed on the safety population.
Pharmacokinetic (PK)	The PK population includes all participants in the safety population with at least one non-missing result for functional dupilumab concentration in serum after first dose of the study treatment. Participants will be analyzed according to the intervention actually received.
Antidrug antibody (ADA)	ADA population includes all participants in the safety population who have at least one non-missing ADA result after first dose of the study treatment. Participants will be analyzed according to the intervention actually received.

ADA: antidrug antibody; ICF: informed consent form; ITT: intent to treat; PD: pharmacodynamics; PK: pharmacokinetic.

Participants exposed to study intervention before or without being randomized will not be considered randomized and will not be included in any analysis population. The safety experience of these participants will be reported separately.

Randomized participants for whom it is unclear whether they took the study intervention will be considered as exposed and will be included in the safety population as randomized.

For any participant randomized more than once, only the data associated with the first randomization will be used in any analysis population. The safety experience associated with any later randomization will be reported separately.

For participants receiving more than one study intervention (placebo and dupilumab) during the study, the intervention group for as-treated analysis will be the dupilumab group.

Regarding the COVID-19 pandemic, additional summaries by COVID-19 subgroups (i.e., impacted by the COVID-19 pandemic and NOT impacted by the COVID-19 pandemic) will be provided to assess the impact of COVID-19 on treatment effect. Participants impacted by the COVID-19 pandemic are defined as randomized participants with any critical or major deviation related to COVID-19 or who permanently discontinued study intervention or study due to COVID-19.

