**Table 5 - Populations for analyses**

Population	Description
Screened	All participants who sign the ICF.
Randomized	The randomized population includes all participants with a treatment kit number allocated and recorded in the IRT database, and regardless of whether the treatment kit was used or not. Participants treated without being randomized will not be considered randomized and will not be included in any efficacy population.
Intent-to-treat (ITT)	All randomized participants analyzed according to the treatment group allocated by randomization regardless if treatment kit is used or not
Efficacy	The ITT population
Safety	All participants randomly assigned to study intervention and who take at least 1 dose of study intervention. Participants will be analyzed according to the intervention they actually received. Randomized participants for whom it is unclear whether they took the study medication will be included in the safety population as randomized. For participants who accidentally receive different treatment from the planned, the actual intervention allocation for as-treated analysis will be the dupilumab group. The PD analyses will be performed on the safety population.
Pharmacokinetic (PK)	The PK population includes all participants in the safety population with at least one non-missing result for functional dupilumab concentration in serum after first dose of the study treatment. Participants will be analyzed according to the intervention actually received.
Antidrug antibody (ADA)	ADA population includes all participants in the safety population who have at least one non-missing ADA result after first dose of the study treatment. Participants will be analyzed according to the intervention actually received.

ADA: antidrug antibody; ICF: informed consent form; ITT: intent to treat; PD: pharmacodynamics; PK: pharmacokinetic

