## 1 INTRODUCTION

### 1.1 STUDY DESIGN

This study is a multi-center, 24-week treatment, parallel group, double-blind, randomized, placebo-controlled study to evaluate the use of dupilumab in participants with prurigo nodularis (PN) inadequately controlled on topical prescription therapies or when those therapies are not advisable. The study will assess the effect of dupilumab on itch improvement as well as its effect on PN lesions, on participants' health-related quality of life (HRQoL), anxiety and depression, sleep quality, skin pain, and overall health status.

After 2-4 weeks of screening, participants will be centrally randomized using a permuted block randomization schedule via Interactive Voice Response System/Interactive Web Response System (IVRS/IWRS) in a 1:1 randomization ratio to dupilumab 300 mg q2w or matching placebo.

Randomization will be stratified by documented history of atopy (atopic or non-atopic), stable use of topical corticosteroids (TCS)/ topical calcineurin inhibitors (TCI) (yes or no), and country/territory code.

A total of approximately 150 participants will be randomized to two treatment arms (75 participants/arm). The number of participants with active mild AD upon study entry will represent up to 10% of the atopic participants. Both the atopic and the non-atopic PN populations will each be capped at 60% of the total enrolled population.

The study duration consists of the following periods:

- Screening period (2-4 weeks)
- Randomized IMP intervention period (24 weeks)
- Follow-up period (12 weeks)

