## **4.7 SAFETY ANALYSES**

All safety analyses will be performed on the safety population as defined in [Section 3](#), unless otherwise specified, using the following common rules:

- The analysis of the safety variables will be descriptive, and no testing is planned.
- Safety data in participants who do not belong to the safety population (e.g., exposed but not randomized) will be provided separately.

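### The wrong-treatment sentence in the Safety population puts a participant randomised to dupilumab who took only placebo into the dupilumab group

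*SAP*

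**What the plan says.** The Safety row of SAP Table 4 carries two allocation rules in one cell. The general rule, worded identically in protocol Table 5, is "Participants will be analyzed according to the intervention they actually received". The rule for errors follows: "For participants who accidentally receive different treatment from the planned, the actual intervention allocation for as-treated analysis will be the dupilumab group". Protocol Table 5 repeats this too, so the two documents agree with each other.

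The text below SAP Table 4 adds a rule on mixed exposure: anyone who was given both placebo and dupilumab in the course of the trial counts as dupilumab in the as-treated analysis.

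The PK and ADA rows of SAP Table 4 carry only a received-treatment rule, "Participants will be analyzed according to the intervention actually received", with no dupilumab default of their own.

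On reach, SAP section 4.7 refers to SAP section 3 and allows stated exceptions: "All safety analyses will be performed on the safety population as defined in". The Safety row also assigns the pharmacodynamic analyses to this population, and SAP section 4.8.3 plots total IgE by intervention group.

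**The concern.** An as-treated grouping should separate people who had the drug from people who did not. Counting anyone with some dupilumab exposure as dupilumab is the usual cautious convention. Counting someone with none is not: it adds an unexposed person to the dupilumab denominator and removes a placebo-treated person from the comparator.

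As worded, the error rule depends neither on the direction of the mistake nor on any dupilumab dose. A programmer who follows the cell literally has two instructions that disagree for one type of participant. The affected outputs are the adverse-event tables, the rates per 100 patient-years (SAP section 4.7.2) and the total IgE summaries. If the wording stays as it is, someone may have to choose that participant's group once kit contents and adverse events are both known.

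**Working it through.** The plan gives no figure on this point, so there is none to reproduce. The check has two parts.

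**1. Apply each rule to the four wrong-treatment cases.**

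| Randomised to | Received | Error rule in Table 4 | Received-treatment rule | Rule below SAP Table 4 |
|---|---|---|---|---|
| Dupilumab | Placebo only | Dupilumab | Placebo | Silent |
| Dupilumab | Both | Dupilumab | Not decisive alone | Dupilumab |
| Placebo | Dupilumab only | Dupilumab | Dupilumab | Silent |
| Placebo | Both | Dupilumab | Not decisive alone | Dupilumab |

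Only the first row conflicts.

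**2. Size the effect of one first-row participant.**

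Inputs: 75 participants per arm (SAP section 1.1). I assume that all are treated and that exactly one is a first-row case. Let *x* be the dupilumab-group participants with a given event when this person is counted there, *y* the placebo-group participants with it, and *e* = 1 if this person has the event, otherwise 0.

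- Error rule as written: *x*/75 on dupilumab and *y*/75 on placebo.
- Grouped by treatment received: (*x* − *e*)/74 on dupilumab and (*y* + *e*)/76 on placebo.

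Shift in dupilumab incidence, *x*/75 − (*x* − *e*)/74:
- *e* = 1: (75 − *x*)/5550, never negative. The largest value is at *x* = 1: 74/5550 = 1.33 points.
- *e* = 0: −*x*/5550, never positive. The extreme is at *x* = 74: −74/5550 = −1.33 points.

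Shift in placebo incidence, *y*/75 − (*y* + *e*)/76:
- *e* = 1: (*y* − 75)/5700, with its extreme at *y* = 0: −75/5700 = −1.32 points.
- *e* = 0: *y*/5700, with its extreme at *y* = 75: 75/5700 = +1.32 points.

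Shift in the difference (dupilumab minus placebo):
- *e* = 1: at most 1.33 + 1.32 = 2.65 points upward.
- *e* = 0: at most 1.33 + 1.32 = 2.65 points downward.

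Enumerating all event counts gives the same maxima: 1.33, 1.32 and 2.65 points. These are worst cases at extreme event counts; other counts give smaller shifts.

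**The case against.** The strongest reply is that the SAP section already contains the right answer. The rule below Table 4 sends mixed exposure to dupilumab. Read with the received-treatment sentence, it implies any dupilumab to dupilumab and placebo only to placebo. That is probably what was meant, and it shows that the remedy agrees with the authors' intent. It does not remove the conflict: the lower rule is silent on placebo-only participants, nothing gives it priority over the table, and protocol Table 5 has no such rule beneath it.

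It is also fair that little depends on this. Safety analysis is descriptive with no testing (SAP section 4.7), efficacy uses the ITT population, and nothing in the documents suggests that a case has occurred. All of that stands and limits the severity.

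Four stronger readings are tempting, and the documents do not support them.

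- *Every dosing error is affected.* The sentence covers receipt of a different treatment, not missed doses or overdoses.
- *One wrong kit on Day 1 is enough.* Each kit holds one syringe (protocol Table 2), and Day 1 requires two injections (protocol section 1.1). With one wrong kit and one correct kit, a participant randomised to dupilumab receives both treatments and is properly counted as dupilumab. The conflict needs every administered dose to be placebo.
- *Dupilumab concentration summaries would be biased downward.* The PK row has its own received-treatment rule, under which this person is summarised as placebo. A bias would require carrying the Safety default into PK, which the text does not say. Its size would also need an assay limit and trough level that the documents do not give.
- *Unequal group sizes across safety, PK and ADA tables would reveal an error.* The PK and ADA populations each require a non-missing post-dose result, so their sizes can differ from the safety population anyway.

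**Conclusion.** The point holds as a minor wording error that gives a wrong allocation when followed. In one of four wrong-treatment cases, a person with no dupilumab exposure is reported as dupilumab-exposed in the safety and pharmacodynamic summaries, against the sentence just before it in the same cell.

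One such participant moves descriptive incidence by at most 1.3 points on dupilumab and the between-group difference by at most about 2.7 points, assuming 75 treated per arm. It is not simply dilution: dupilumab incidence is pulled down if that person has no event and pushed up if they do. The primary and key secondary results do not change, and the SAP does not depart from the protocol here. What remains across populations is that the Safety row has the default while the PK and ADA rows do not, so the same person could be labelled differently in different tables.

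**What to change.** In the Safety row of SAP Table 4, replace the error sentence with: *Participants who receive at least one dose of dupilumab, alone or with placebo, are analysed in the dupilumab group; participants who receive only placebo are analysed in the placebo group.* State that the PK and ADA populations use the same assignment. Make the same replacement in protocol Table 5 at the next amendment.

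The new sentence agrees with the rule already given below SAP Table 4 and leaves three of the four cases where they are. In the fourth, one participant would change the safety denominators from 75 and 75 to 74 dupilumab and 76 placebo. The cost is one sentence in each document plus a short cross-reference, with no new data. It should be settled before the primary database lock.

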### **Methods of assigning patients to treatment group**

The randomized intervention kit number list is generated centrally by Sanofi and IMPs are packaged in accordance with this list. The randomization and intervention allocation are performed centrally by an IRT. The IRT generates the participant randomization list and allocates the intervention number and the corresponding intervention kits to the participants according to it.

Participants will be randomized in 1:1 ratio to treatment arms described in [Table 2](#).

Randomization will be stratified by the following factors:

- documented history of atopy (atopic or non-atopic)
  - Atopic: Patients with a physician-documented history of atopic comorbidities defined as AD, allergic rhinitis/rhinoconjunctivitis, asthma, or food allergy, or a current diagnosis of at least one of these atopic comorbidities, per investigator judgement.  
NOTE: enrollment of patients with a current diagnosis of active mild AD will be capped at up to 10% of the participants in this subgroup
  - Non-atopic: Patients without a physician-documented history of atopic comorbidities defined as AD, allergic rhinitis/rhinoconjunctivitis, asthma or food allergy, and without a current diagnosis of at least one of such atopic comorbidities, per investigator judgement
- stable use of TCS/TCI (yes or no)
- country/territory code

A randomized participant is defined as a participant who has been allocated to a randomized intervention regardless whether the intervention kit was used or not (ie, participant registered by the IRT).

A participant cannot be randomized more than once in the study.

Study intervention will be dispensed at the study visits summarized in SoA (see [Section 1.3](#)). Returned study intervention should not be re-dispensed to the participants.

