## Analysis windows for time points

### *Efficacy assessment*

For the efficacy assessment, the reference date for the derivation of relative days of events or findings will be the randomization day. If a participant receives IMP prior to the randomization by mistake, the reference date of efficacy assessment will be the date of the first IMP administration for that participant.

For daily eDiary data (WI-NRS, skin Pain-NRS, Sleep-NRS), all available values of daily measurements will be assigned to each week window according to [Table 10](#), and then weekly average score will be calculated. Randomization day is used as the reference day (Day 1).

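### The SAP text below Table 4 excludes participants dosed before randomization even if they are later randomized, which is wider than the population definitions in Table 4 and in the protocol

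*SAP*

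**What the plan says.** SAP Section 3, Table 4, builds its populations on IRT allocation:

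- Randomized: "The randomized population includes all participants with a treatment kit number allocated and recorded in the interactive response technology (IRT) database".
- ITT, which is also the efficacy population: "All randomized participants analyzed according to the intervention group allocated by randomization regardless if treatment kit is used or not".
- Safety: "All participants randomly assigned to study intervention and who take at least 1 dose of study intervention".
- PK and ADA are subsets of Safety, each requiring a non-missing result after the first dose.

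None of these sets a condition on the order of first dose and randomization. The one exclusion in the Randomized row is worded as in protocol Section 9.3, Table 5: "Participants treated without being randomized will not be considered randomized and will not be included in any efficacy population". Protocol Section 6.3 agrees: "A randomized participant is defined as a participant who has been allocated to a randomized intervention regardless whether the intervention kit was used or not".

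The text below SAP Table 4 goes further: "Participants exposed to study intervention before or without being randomized will not be considered randomized and will not be included in any analysis population". The next sentence says that the safety experience of these participants will be reported separately, and SAP Section 4.7 repeats this for anyone outside the safety population.

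SAP Section 5.4 (Appendix 4, efficacy assessment) has a rule for the same situation: "If a participant receives IMP prior to the randomization by mistake, the reference date of efficacy assessment will be the date of the first IMP". The following paragraph, on daily eDiary data, makes randomization day Day 1 and does not repeat that exception. SAP Section 4.1 takes the WI-NRS baseline from the 7 days before randomization.

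**The concern.** A participant injected by mistake before IRT registration and then randomized meets the Table 4 definitions of Randomized, ITT and Safety. The sentence below the table declares the same person not randomized and in no population. SAP Section 4.3.2 makes ITT the primary analysis population, so the denominator of the Week 12 responder analysis depends on which statement is followed. Membership of the by-arm safety, PK and ADA populations depends on it too.

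ITT analysis is meant to ensure that a site error does not remove a randomized participant. Neither the SAP version history (Table 1) nor its appendix on changes to protocol-planned analyses (Table 9) mentions a narrower randomized set than the protocol's, so nothing shows that the departure was intended. It should be settled before database lock rather than when a case appears.

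**Working it through.** No figure in the plan is at issue, so the check is mainly a comparison of texts.

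**1. One test case.** Take a participant dosed by mistake *d* days before IRT randomization and then randomized.

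| Rule | What it turns on | Result |
|---|---|---|
| Protocol 6.3 | IRT allocation | randomized |
| Protocol 9.3, Table 5 | kit recorded in IRT; out only if never randomized | in |
| SAP Table 4, Randomized | same | in |
| SAP Table 4, ITT/Efficacy | randomized, as allocated | in |
| SAP Table 4, Safety | randomly assigned and at least 1 dose | in |
| SAP Table 4, PK and ADA | Safety plus a post-first-dose result | in if sampled |
| SAP text below Table 4 | dosed before randomization | out of all |
| SAP 5.4 reference date | IMP before randomization | silent on membership; sets an efficacy day count |

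**2. What the extra wording adds.** Participants never randomized are already covered by *without*, so *before* can only add people randomized later. The sentence also extends the exclusion from efficacy populations to every population. For participants never randomized this changes nothing: they already fail Safety, which requires random assignment, and PK and ADA are subsets of Safety. Both extensions therefore bite only on the participant dosed first and randomized afterwards.

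**3. Size per case.** Planned numbers are about 150 in total and 75 per arm (SAP Section 1.1).

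- Share of the trial: 1/150 = 0.67%.
- Share of an arm: 1/75 = 1.33%.
- Effect on an arm's response rate, with *x* responders among 75:
  - Dropping a non-responder changes it by x/74 − x/75 = x/5550, at most 74/5550 = 1.33 percentage points.
  - Dropping a responder changes it by x/75 − (x − 1)/74 = (75 − x)/5550, again at most 74/5550 = 1.33 points.

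**4. What happens if the participant is kept.** Two eDiary rules then matter for the primary endpoint.

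- Baseline: of the 7 diary days before randomization, *d* fall on or after the dosing day (for d ≤ 7), a share of d/7. The general efficacy baseline in SAP Section 4.1 must precede both randomization and first dose. The eDiary baseline carries only the randomization condition.
- Windows: SAP Table 10 sets Week 12 at Days 82 to 88. If Day 1 is randomization, those days are 82 + d to 88 + d when counted from first dose. The first-IMP reference date and the eDiary Day 1 sentence thus place the window *d* days apart.

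If itch falls after the early dose, a baseline that includes those days is too low and a reduction of at least 4 points is harder to reach. Deleting two words from Section 3 would not resolve this.

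**The case against.** The strongest defence is that the sentence below Table 4 says who counts as randomized, so it can be read as a specific qualification of the table. A programmer would probably apply the explicit exclusion, which makes the outcome less open than the comparison suggests. That has some force. But the qualification contradicts the protocol's definition of a randomized participant and comes with no justification.

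Four stronger readings are tempting, and the documents do not support them.

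- A reader might infer a biased treatment comparison from a post-randomization exclusion. The trigger is a dose given before allocation, so it cannot depend on the assigned arm or on later outcome. What is shown is a departure from the full randomized set.
- A reader might infer that safety data are lost. SAP Sections 3 and 4.7 both provide for separate reporting. What is lost is the participant's place in the by-arm safety population.
- A reader might infer that Appendix 4 is a competing inclusion rule. It sets a date and does not address membership, and a relative-day rule could also serve listings. Under the exclusion it is left without use in the efficacy analyses. The direct conflict is between Table 4 and the text beneath it.
- A reader might infer that cases are expected because the SAP provides for them. That shows the case was foreseen. The documents give no expected count, and protocol Section 6.3 has the IRT allocate kits centrally, so the usual route to a kit is through randomization.

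**Conclusion.** The inconsistency holds. The sentence below SAP Table 4 is wider than the Randomized, ITT and Safety definitions above it and than protocol Sections 6.3 and 9.3. It would drop a participant dosed by mistake and then randomized from the ITT primary analysis and the by-arm safety population. Excluding participants who are never randomized agrees with the protocol and is not in question.

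At the planned 75 per arm, one case is 1.3% of an arm and moves that arm's response rate by at most 1.3 percentage points. How many cases arise is unknown. With central IRT allocation the event should be rare, and nothing here suggests that the trial's conclusion would change. The point is a departure from the plan's own ITT set and an unsettled denominator, cheap to correct before database lock.

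**What to change.** In SAP Section 3, delete *before or*, so that the exclusion covers only participants never randomized. State that anyone with an IRT randomization record stays in ITT as allocated, in Safety if dosed, and in PK and ADA if the sample criteria are met. The SAP's existing as-treated rules then apply to the safety analyses.

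Make two further edits at the same time, for participants dosed before randomization:

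- In Section 4.1, end the eDiary baseline window at the first IMP date, so that baseline WI-NRS uses only pre-dose days.
- In Section 5.4, give the eDiary Day 1 sentence the same first-IMP exception as the general efficacy reference date, so that Table 10 is counted from one origin.

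If the sponsor does intend the exclusion, the SAP should instead remove the first-IMP reference-date rule, list the departure from the protocol's populations and justify it.

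Either route costs a few sentences in the SAP and the matching programming, with no change to trial conduct.
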